### **5.3. Sample size**

Due to the rarity of the disease and the single-center design of the Treatment Outcomes of DOACs in CVT study, a minimum of 69 patients are expected to be enrolled over a 2-year period starting in June 2025. Patient recruitment is anticipated to be completed by June 2027, with final 6-month follow-up assessments expected to conclude by December 2027.

## **6. STATISTICAL ANALYSES**

All statistical analyses will be conducted using R software (version 4.4.1). Statistical significance will be set at a two-sided p-value < 0.05.

Descriptive statistics will be used to summarize baseline characteristics. Continuous variables will be reported as means  $\pm$  standard deviations (SD) or medians with interquartile ranges (IQR), depending on distribution. Categorical variables will be expressed as counts and percentages.

The primary endpoint: a composite of major bleeding (per ISTH criteria) or symptomatic recurrent venous thromboembolism (VTE), including cerebral venous thrombosis, deep vein thrombosis, pulmonary embolism, or splanchnic vein thrombosis—will be analyzed as a time-to-event outcome. Kaplan–Meier survival curves will be constructed, and group comparisons will be performed using the log-rank test. Cumulative event rates at 6 months will be reported with 95% confidence intervals.

For secondary endpoints, the following analyses will be conducted:

- Functional outcome (mRS 0-1 vs 2-6 at 3 and 6 months) will be analyzed using logistic regression to identify predictors of favorable recovery.

- Venous recanalization status at 6 months will be described as complete, partial, or absent, based on follow-up imaging, and summarized as proportions.
- Rates of major bleeding, any bleeding, symptomatic recurrent VTE, and arterial thrombotic events will be summarized descriptively and reported with 95% confidence intervals.
- Health-related quality of life (EQ-5D-5L), chronic post-CVT headache (HIT-6), at 3 and 6 months will be compared using paired t-tests or Wilcoxon signed-rank tests, as appropriate.
- Changes in D-dimer levels from baseline to follow-up will be analyzed using paired tests and visualized longitudinally.

Missing data will be handled using complete case analysis. If the missing rate exceeds 10% for any variable, sensitivity analyses will be performed.

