## SUMMARY

**Rationale:** Cerebral venous thrombosis (CVT) is a rare condition. Once the diagnosis is established, current guidelines consistently recommend the early initiation of anticoagulation therapy with heparin, even in the presence of intracerebral hemorrhage. Upon clinical and radiological stabilization, treatment is typically transitioned to oral anticoagulants, including either vitamin K antagonists (VKA) or direct oral anticoagulants (DOACs). Since 2019, emerging evidence from randomized controlled trials such as RESPECT-CVT, CHOICE-CVT, and SECRET, along with large-scale international observational studies including ACTION-CVT and DOAC-CVT has demonstrated that DOACs can be safely used in the treatment of CVT. However, due to the rarity of the condition, most existing studies are limited by small sample sizes. Therefore, there is a growing need for additional studies across diverse geographic regions to expand the global evidence base on DOACs use in CVT. Such data will help enable more accurate assessment and analysis of treatment outcomes in patients with CVT receiving DOACs therapy.

**Objective:** To evaluate treatment outcomes of DOAC therapy in CVT patients.

**Study Design:** A prospective cohort study at Bach Mai Hospital, Vietnam, enrolling a minimum of 69 patients with CVT treated with DOACs.

**Study Population:** Adult patients ( $\geq 18$  years old) with radiologically confirmed CVT, treated with therapeutic-dose heparin in the acute phase and subsequently with a direct oral anticoagulant. All will be recruited from Bach Mai Hospital, the national referral center for CVT in northern Vietnam.

**Primary study endpoint:** the primary endpoint is a composite of the number of patients who experience either major bleeding, as defined by the International Society on Thrombosis and Haemostasis (ISTH), or a venous thromboembolic event (VTE) - including recurrent CVT, deep vein thrombosis of any limb, pulmonary embolism, or splanchnic vein thrombosis — within up to 6 months of follow-up.

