**The secondary endpoint:**

- Mortality Rate: all death from any cause during the 6-month follow-up.
- Functional outcome: proportion of patients with mRS 0–1 at 3 and 6 months.
- Number of participants with major bleeding events
- Number of participants with clinically relevant non-major bleeding (CRNMB) events
- Number of participants with symptomatic recurrent venous thromboembolism (VTE)
- Number of participants who discontinued anticoagulant therapy early
- Number of participants with arterial thrombotic events
- Number of participants with arterial thrombotic events
- Serial D-dimer measurements after CVT
- Venous recanalization
- Frequency of chronic headache after CVT

**Nature and Extent of Risks, Burdens, and Benefits:** This study is non-interventional in nature and does not introduce any additional procedures, risks, or burdens for participants. All information utilized will be obtained exclusively from standard clinical care and follow-up, without altering the course of treatment. No experimental interventions will be administered, and participation does not affect patients' access to care or outcomes.

ClinicalTrials.gov Identifier:

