## **2. OBJECTIVE**

### **Primary Objective**

To evaluate the effectiveness and safety of DOACs in patients with CVT over a 6-month follow-up period, using the composite outcome of major bleeding events or recurrent venous thromboembolism.

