## 5. METHODS

### 5.1. Study endpoint

#### 5.1.1. Primary study endpoint

The primary endpoint of the study is a composite outcome assessed over a 6-month follow-up period, comprising: (1) the occurrence of VTE, including recurrent CVT, deep vein thrombosis of any limb, pulmonary embolism, or thrombosis involving the splanchnic, jugular, caval, renal, or catheter-related veins; and (2) major bleeding events, defined according to the criteria established by the International Society on Thrombosis and Haemostasis (ISTH) (see Appendix B).

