#### 5.1.2. Secondary study endpoint

##### **Assessed at 3 and 6 months ( $\pm$ 1 month):**

- Functional outcome: defined as a score of 0–1 on the Modified Rankin Scale (mRS). The mRS ranges from 0 (no symptoms) to 6 (death). Lower scores reflect better functional recovery.
- Number of participants with major bleeding events: defined according to the criteria established by the International Society on Thrombosis and Haemostasis (ISTH) (see Appendix B)
- Number of participants with clinically relevant non-major bleeding (CRNMB) events: defined according to the criteria established by the International Society on Thrombosis and Haemostasis (ISTH) (see Appendix B)
- Number of participants with symptomatic recurrent VTE
- Health-related quality of life, measured by the EQ-5D-5L instrument and the Vietnamese population value set validated by Mai et al.
- Serial D-dimer measurements after CVT: plasma D-dimer levels will be measured at 3 and 6 months using a standardized quantitative assay. Values will be reported in ng/mL and interpreted in the context of post-CVT coagulation activity

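### Section 6 names only Kaplan-Meier for a composite that leaves out death from other causes; if such a death precedes a later event, the 6-month rate slightly overstates the share of patients with an event.

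*Protocol*

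**What the plan says.** The Summary states the primary endpoint as a count of patients: "the primary endpoint is a composite of the number of patients who experience either major bleeding", or a venous thromboembolic event, within up to 6 months. The Primary Objective in Section 2 says the drugs will be evaluated "using the composite outcome of major bleeding events or recurrent venous thromboembolism". Section 5.1.1 counts "the occurrence of VTE, including recurrent CVT, deep vein thrombosis of any limb, pulmonary embolism" and other venous sites, together with ISTH major bleeding.

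Section 6 says this composite "will be analyzed as a time-to-event outcome". It calls for Kaplan-Meier curves, with a log-rank test for group comparisons, and continues: "Cumulative event rates at 6 months will be reported with 95% confidence intervals". No other estimator is named for the primary endpoint, and the section does not say how a patient who dies is handled.

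All-cause death is in none of the statements of the composite. It is a separate secondary endpoint, given in the Summary as "all death from any cause during the 6-month follow-up". Some deaths are nevertheless primary events: Appendix B lists fatal bleeding under major bleeding, and a fatal VTE is an occurrence of VTE under Section 5.1.1. Only deaths from neither cause fall outside.

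**The concern.** A patient who dies of another cause can no longer have a major bleed or a VTE. Kaplan-Meier, left at its default, treats that patient as censored, that is, as someone who could still have the event at the same rate as those who remain. The quantity 1 minus Kaplan-Meier then estimates the risk in a hypothetical setting without other deaths. The Summary asks for something else: how many of the enrolled patients have an event. The two differ only when an other-cause death comes before a later event, and then Kaplan-Meier is always the higher.

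The 6-month rate, with its interval, is the main result of an analysis that Section 8 says will focus on the DOAC patients. It should estimate the quantity the endpoint definition names.

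**Working it through.** **Inputs.** From the protocol: n = 69 (Section 5.3, a minimum), a 6-month horizon, the composite and the estimator as set out above. The protocol gives no event rate, death rate or precision target, so there is no figure of its own to reproduce. The rates below are assumptions. F is the true share of patients with a primary event by 6 months, and D is the share who die of another cause first.

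**Step 1, constant hazards.** Total cumulative hazard H = -ln(1 - F - D). Event part h = H x F/(F + D). With other deaths censored, 1 minus Kaplan-Meier = 1 - exp(-h). For F = 5%, D = 5%: H = -ln(0.90) = 0.1054, h = 0.0527, and 1 - exp(-0.0527) = 5.13%. The excess is 0.13 points, or 0.09 of a patient in 69.

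**Step 2, upper bound.** If every other death comes before every event, 1 minus Kaplan-Meier = F/(1 - D). For F = 5%, D = 5%: 0.05/0.95 = 5.26%, an excess of 0.18 of a patient.

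| True F | Other deaths D | 1 - KM, constant hazards | Excess, patients of 69 | 1 - KM, all deaths first | Excess, patients of 69 |
|---|---|---|---|---|---|
| 5% | 3% | 5.08% | 0.05 | 5.15% | 0.11 |
| 5% | 5% | 5.13% | 0.09 | 5.26% | 0.18 |
| 5% | 10% | 5.27% | 0.19 | 5.56% | 0.38 |
| 10% | 10% | 10.56% | 0.38 | 11.11% | 0.77 |

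**Step 3, lower bound.** If all other deaths come after the last event, or none occur, the excess is zero.

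**Step 4, check by counting.** Take 69 patients, 4 events, 3 other deaths and no loss to follow-up.
- Deaths before the first event: 66 patients are at risk when events begin, so 1 minus Kaplan-Meier = 4/66 = 6.06%.
- Deaths after the last event: 1 minus Kaplan-Meier = 4/69 = 5.80%.
- Aalen-Johansen gives 4/69 = 5.80% in both orders, which is the share of patients with an event.

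**Step 5, scale.** The exact 95% interval is 1.6% to 14.2% for 4/69 and 4.2% to 19.8% for 7/69. Against these, the constant-hazard excess is 0.08 to 0.27 points at F = 5% and 0.56 points at F = 10%.

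**Step 6, beyond the assumed range.** With F = 15% and D = 10%, constant hazards give 15.85% (0.59 of a patient). The all-deaths-first bound gives 16.67%, which is 1.67 points or 0.0167 x 69 = 1.15 patients. The exact interval for 10/69 is 7.2% to 25.0%, so even this lies well inside sampling error.

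**The case against.** The strongest objection is that censoring and competing-event rules usually belong in a statistical analysis plan, which is not at hand. Section 6 asks for Kaplan-Meier curves in one sentence and promises the rates in the next, without naming an estimator there. That the rates are 1 minus Kaplan-Meier, and that other deaths are censored, are both inferences. This is fair, and it is why the point is worded conditionally. It does not remove the point. The protocol is not silent on method: it names one for the primary endpoint and no other, and an analysis plan that followed it would carry the mismatch forward.

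Second, the effect is tiny and the death rates are assumed. Both are true. A reader might infer that the protocol expects deaths, because mortality is an endpoint and the mRS includes a category for death. Listing an endpoint or describing a scale predicts no number of deaths. Section 4.2 also requires a DOAC to be started 5 to 15 days after heparin, so patients who die before starting one never enter the cohort.

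Third, Section 6 also reports bleeding and VTE rates descriptively, and mortality is a separate endpoint, so a reader of the results could partly see any gap. That lowers the risk of being misled but does not supply the composite rate.

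A reader might also infer a further bias from the sentence "Missing data will be handled using complete case analysis", taking it to drop patients lost before 6 months. The document does not support that reading for this endpoint: Section 6 specifies a time-to-event analysis, which handles incomplete follow-up by censoring. That is not part of this point.

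**Conclusion.** The point holds in conditional form and is minor. The only estimator named for the primary composite does not match the endpoint as the Summary defines it. If an other-cause death precedes a later event and is censored, the reported 6-month rate is too high, never too low. For assumed rates of 5-10% events and 3-10% other deaths, the excess stays under one patient in 69, and it is zero if no such death occurs.

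This rests on two readings, that the promised rates are 1 minus Kaplan-Meier and that other deaths are censored by default, and on rates that the protocol does not give. A reader might infer that the main result is unreliable. The figures do not support that: the shift is well inside sampling error. It is an inexpensive correction of what is being estimated, to be considered, and not a threat to the study's conclusion.

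**What to change.** In Section 6, state that the 6-month rate of the primary composite and its 95% confidence interval will be estimated as an Aalen-Johansen cumulative incidence, with death from neither bleeding nor VTE as the competing event. State also that fatal bleeding and fatal VTE remain primary events.

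The cost is a sentence or two in the protocol and a standard R routine. The analysis needs dates of event, death and last contact. The downside is slightly more analysis work, and each death must be classed as bleeding, VTE or neither. The composite already requires part of that, because fatal bleeding has to be identified under Appendix B.

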## **Study protocol: Treatment Outcomes of DOACs in CVT: A Prospective Study in Vietnam**

Recent international guidelines now permit the use of either VKAs or DOACs in the treatment of CVT, acknowledging the growing body of evidence indicating similar safety and efficacy profiles. Research in this area remains ongoing worldwide.

In Vietnam, research on CVT treatment outcomes - particularly regarding the use of DOACs - is still limited. Moreover, due to the rarity of the condition and the complexity of evaluating multiple risk factors, patients with CVT are typically referred to major stroke centers for specialized management. Consequently, patient cohorts from such tertiary centers may provide insights that are representative of the national CVT population, rather than being confined to local or institutional patterns.

The primary objective of the present study, Treatment Outcomes of DOACs in CVT, is to evaluate the real-world safety and efficacy of DOACs in the management of CVT in Vietnam. The secondary objective is to assess clinical outcomes and identify factors associated with treatment response during follow-up.

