## **5.2. Study procedures**

Baseline clinical and radiological data, including patient demographics, risk factors, imaging findings, anticoagulant treatment details, and in-hospital events during the acute phase of CVT, will be collected for all enrolled patients.

Participants will be followed up at 3 and 6 months after diagnosis. Data collected at these time points will include:

- Type and duration of oral anticoagulant therapy
- Clinical events, including recurrent thrombotic or bleeding events
- Degree of disability will be assessed using mRS
- Venous recanalization will be assessed at 6 months using brain MRI with venography or CT venography. Recanalization will be categorized as complete, partial, or none, based on the classification proposed by Aguiar de Sousa et al
- Health-related quality of life, evaluated using the EQ-5D-5L instrument. This tool evaluates five domains (mobility, self-care, usual activities, pain/discomfort, and anxiety/depression), each with five levels of severity. A utility index score will be calculated using the Vietnamese EQ-5D-5L value set, ranging from -0.511 to 1.000, where 1.000 indicates perfect health, 0.000 corresponds to death, scores below 0 indicate health states considered worse than death by the general Vietnamese population.
- Presence of chronic headache, defined as a headache occurring on  $\geq 15$  days per month and persisting for more than 3 months following the acute CVT event, consistent with the International Classification of Headache Disorders, 3rd edition

(ICHD-3). Headache-related disability, assessed using the Headache Impact Test (HIT-6)

All data will be collected as part of routine clinical care during outpatient visits or structured telephone interviews and recorded using standardized case report forms.

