### **8. LIMITATIONS**

This study has several limitations. First, it is a single-center investigation conducted at Bach Mai Hospital, a national tertiary referral center. While this may raise concerns regarding generalizability, the hospital receives the majority of CVT cases from a wide geographic area in northern Vietnam, including referrals from provincial and district-level hospitals. Therefore, the study population is expected to be broadly representative of the CVT patient population in real-world clinical practice within the region.

Second, given the rarity of CVT and the fixed 2-year enrollment window, the sample size is expected to be limited. This may reduce the statistical power to perform robust subgroup analyses or develop complex multivariable models. However, the study is designed to maximize data completeness through close follow-up and adherence to protocol-defined procedures.

Third, although the study currently includes both DOAC and VKA group, the planned analysis will primarily focus on the DOAC subgroup. This approach reflects the growing interest in the real-world effectiveness and safety of DOACs in CVT management. Including VKA patients in the recruitment phase may still provide useful contextual information for future comparative analyses.

Finally, some outcome data, such as follow-up imaging for venous recanalization or standardized cognitive assessments, may be unavailable for a small number of patients due to loss to follow-up or logistical constraints. Nonetheless, the study team is committed to minimizing missing data through proactive patient engagement and structured follow-up planning.

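### The search for predictors of mRS 0-1 in about 69 patients can carry only a few parameters; odds ratios may be unstable, and those picked by p<0.05 would be exaggerated

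*Protocol*

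**What the plan says.** Section 6 (Statistical analyses) splits the mRS into 0-1 versus 2-6 at 3 and at 6 months and states that it "will be analyzed using logistic regression to identify predictors of favorable recovery". The same section sets the threshold for the whole study: "Statistical significance will be set at a two-sided p-value < 0.05". It also states: "Missing data will be handled using complete case analysis".

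The closing paragraph of Section 1 gives the purpose. Part of the secondary objective is to "identify factors associated with treatment response during follow-up".

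Section 5.3 states that "a minimum of 69 patients are expected to be enrolled over a 2-year period starting in June 2025". The reasons given are the rarity of the disease and the single-centre design.

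Section 5.2 describes the baseline data from which predictors could come: "patient demographics, risk factors, imaging findings, anticoagulant treatment details, and in-hospital events during the acute phase of CVT".

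Section 8 (Limitations) says of the limited sample size: "This may reduce the statistical power to perform robust subgroup analyses or develop complex multivariable models".

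**The concern.** In logistic regression, the number of patients in the smaller outcome class limits what the model can carry, not the total sample. If most patients recover to mRS 0-1, as few as 7 to 21 of 69 might be in the other class, while the baseline data offer many candidate predictors. Three things can then go wrong:

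- Intervals become very wide and power is low.
- A predictor may separate the outcomes completely, so that the maximum-likelihood odds ratio has no finite value.
- If the factors reported as predictors are those with p<0.05, their odds ratios are exaggerated, because only large estimates can reach significance.

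Section 8 mentions power for complex models. It does not limit the analysis in Section 6 or call it exploratory. At stake is a stated part of the secondary objective. A reader could take a few chance findings, with odds ratios several times too large, as established predictors of recovery after CVT. The primary endpoint is not affected.

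**Working it through.** **Inputs from the protocol.** n = 69 (a minimum, Section 5.3); mRS 0-1 versus 2-6 at two time points, two-sided alpha 0.05 and complete-case analysis (all Section 6).

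**Assumptions.** The protocol gives no rate of mRS 2-6. I take 10%, 20% and 30%, with 50% as a sensitivity case. The protocol does not state the number of predictors either, so 1 to 8 are tried. The guide of 5 to 10 events per parameter is a convention.

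**The plan's own figure.** Section 5.3 gives no rate, effect, power or precision for 69, so it cannot be reproduced. The nearest single-proportion precision formula is 1.96² × 0.5 × 0.5 / 0.12² = 67, but the protocol does not state those inputs.

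**Step 1: parameters supported.** Events = 69 × rate; parameters = events / 10 to events / 5.

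| Rate of mRS 2-6 | Events | At 10 per parameter | At 5 per parameter |
|---|---|---|---|
| 10% | 7 | 0.7 | 1.4 |
| 20% | 14 | 1.4 | 2.8 |
| 30% | 21 | 2.1 | 4.2 |
| 50% | 34 | 3.4 | 6.8 |

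Complete-case analysis can only lower these counts. Enrolment above the minimum would raise them.

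**Step 2: power for one binary predictor split 50/50.** The two risks p0 and p1 are set by their mean (the assumed rate) and the odds ratio. For OR 2 at 30%: p0 = 0.228, p1 = 0.372, difference 0.143, with 34.5 patients per group. The standard error is sqrt(2 × 0.3 × 0.7 / 34.5) = 0.110 under the null and 0.109 under the alternative. Power = Φ((0.143 − 1.96 × 0.110) / 0.109) = 25%. The full set:

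| True OR | 10% | 20% | 30% |
|---|---|---|---|
| 2 | 13% | 20% | 25% |
| 3 | 24% | 41% | 52% |
| 4 | 34% | 57% | 71% |

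**Step 3: can the model be fitted?** Maximum-likelihood fits were simulated with n = 69, independent binary predictors, each with a true OR of 2, and 1,500 to 2,000 runs per setting. Share of fits not estimable (separation or a degenerate predictor):

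| Predictor prevalence | Predictors | 10% | 20% | 30% |
|---|---|---|---|---|
| 30% | 1 | 7% | 0.4% | 0% |
| 30% | 3 | 15% | 1% | 0% |
| 30% | 5 | 23% | 2% | 0.1% |
| 30% | 8 | 36% | 3.5% | 0.1% |
| 10% | 1 | 32% | 11% | 6% |
| 10% | 3 | 64% | 31% | 17% |
| 10% | 5 | 81% | 43% | 27% |

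**Step 4: inflation without selection.** Among estimable fits at prevalence 30% and rates of 10-30%, the typical OR for a true 2 was 1.96 to 2.31, so at most about 15% too high (2.31 / 2 = 1.155). Intervals were wide: the upper limit was about 30 to 68 times the lower at 10% unfavourable, and 9 to 17 times at 30%.

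**Step 5: inflation with selection at p<0.05.** A Wald interval excludes 1 only if the OR exceeds the square root of its upper/lower ratio. With one predictor at 30% unfavourable the ratio is 9.4, so an estimate must exceed √9.4 = 3.1. At 10% the ratio is 29.6 and the bar is √29.6 = 5.4. A true OR of 2 can therefore only be declared significant when it is overestimated. Simulated median of the significant ORs, true value 2, prevalence 30%:

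| Predictors | 10% | 20% | 30% |
|---|---|---|---|
| 1 | 6.6 | 4.6 | 3.9 |
| 3 | 8.7 | 5.3 | 4.7 |
| 5 | 12.2 | 5.9 | 5.1 |

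**Step 6: what Firth's method adds.** In a separate simulation (n = 69, true OR 3, one normal predictor and the rest binary at prevalence 35%, 1,500 runs), six predictors with about 8 events gave separation in 25% of data sets. The median maximum-likelihood OR was 3.7 (10th to 90th percentile 1.1 to 18.4), against 2.9 (1.1 to 8.7) with Firth. With six predictors and about 12 events, separation was 7% and the medians were 3.5 and 2.9. With two predictors and about 12 events, separation was 0.5% and the maximum-likelihood median was 3.1. A further simulation at prevalence 30% found Firth's error below that of maximum likelihood in every setting tried.

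**The case against.** The strongest reply is that Section 6 says little more than logistic regression. It does not say that the fit is by plain maximum likelihood, that the model is multivariable, or that predictors are screened by p-value. Firth's method is itself logistic regression, so the text does not exclude it. The estimator and the covariate list are commonly left to a statistical analysis plan, which may exist. The event rate is assumed, and 69 is a minimum. Section 8 already discloses the small sample.

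Much of this stands, and it limits the point. The absence of a covariate list is no finding. A reader might infer that the odds ratios will be inflated or not estimable. The documents and figures do not support that: at 14-21 events with common predictors nearly every model can be fitted, and average inflation is mostly modest. A reader might also infer that Section 8 concedes that the data cannot support the method. It concedes only reduced power for subgroup analyses and complex models. Nor can power be set aside as a minor harm, because low power combined with selection is what produces the exaggeration.

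What remains is the combination that the protocol does state: identifying predictors as the purpose, a 0.05 threshold, two time points and about 69 patients. Single-predictor models are not a full escape, as the rows for rare predictors in step 3 show. The caveat in Section 8 neither limits the search nor marks it as exploratory.

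**Conclusion.** The point holds as a cheap improvement to one secondary analysis. If 10-30% of patients have mRS 2-6, the data support about one to four parameters; even at 50% they support only about three to seven. Maximum-likelihood estimates may be unstable, mainly near 7 events or with rare predictors. The exaggeration after selection is the most robust harm: with common predictors, a true OR of 2 appears as about 4-5 at 30% unfavourable and about 6.6-12 at 10%.

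These sizes rest on the assumed outcome rate, the assumed number and prevalence of independent predictors, an analysed sample of 69, and significance being used to decide which predictors are reported. The last is a natural reading of the stated purpose and threshold, but the protocol does not spell it out.

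**What to change.** In Section 6, state that:

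- the mRS model will be fitted by Firth penalised logistic regression with profile-likelihood confidence intervals;
- a small number of baseline predictors will be fixed before outcome data are seen, with about one parameter per 5 to 10 patients in the smaller outcome group. A ranked list would let the final number follow from the overall outcome count alone;
- predictors will not be selected by p-value;
- the analysis is exploratory.

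The parts do different work. Firth's method deals with separation and small-sample bias, while fixing the predictors without selection removes the exaggeration in step 5. The exact number of predictors is a matter of judgement within the 5-to-10 guide.

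The cost is a change of wording and a standard package in R, which the protocol already uses. No new data are needed. The downside is that fewer candidate predictors are reported.

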### **Secondary Objectives**

Patients with CVT treated with DOACs will be assessed at 3 and 6 months to determine the following clinical outcomes:

- Mortality Rate
- Functional outcome
- Number of participants with major bleeding events
- Number of participants with clinically relevant non-major bleeding (CRNMB) events
- Number of participants with symptomatic recurrent venous thromboembolism (VTE)

[figure not shown]

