## **Study protocol: Treatment Outcomes of DOACs in CVT: A Prospective Study in Vietnam**

- Venous recanalization
- Number of participants who discontinued anticoagulant therapy early
- Number of participants with arterial thrombotic events
- Frequency of participants with chronic headache after CVT
- Health-related quality of life (EQ-5D-5L utility index score)
- Serial D-dimer measurements after CVT

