### 3. STUDY DESIGN

*Treatment Outcomes of DOACs in CVT* is a prospective, single-center observational study. The study involves the collection of treatment data during both the acute hospitalization phase and subsequent outpatient follow-up. It was conducted at Bach Mai Hospital, a central and tertiary referral center for the management of cerebral venous thrombosis (CVT) in Vietnam.

A schematic diagram of the study design and follow-up is provided below

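### Does the planned test of D-dimer change from baseline lack a baseline value?

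*Protocol*

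**What the plan says.** Section 6 commits to an analysis: "Changes in D-dimer levels from baseline to follow-up will be analyzed using paired tests and visualized longitudinally". The endpoint definition in Section 5.1.2, under the 3- and 6-month heading, says that "plasma D-dimer levels will be measured at 3 and 6 months using a standardized quantitative assay", and gives ng/mL as the reporting unit. The Secondary Objectives introduce their list with "Patients with CVT treated with DOACs will be assessed at 3 and 6 months to determine the following clinical outcomes", and the list includes "Serial D-dimer measurements after CVT".

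For baseline, Section 5.2 names "Baseline clinical and radiological data, including patient demographics, risk factors, imaging findings, anticoagulant treatment details, and in-hospital events during the acute phase of CVT". No laboratory value is among the examples. The same section states that "All data will be collected as part of routine clinical care during outpatient visits or structured telephone interviews", and the Summary says that "All information utilized will be obtained exclusively from standard clinical care and follow-up".

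Section 3 describes data collection as covering both the acute admission and the outpatient period, and adds: "A schematic diagram of the study design and follow-up is provided below". That figure is not shown in the text at hand. Section 6 applies complete-case analysis and calls for sensitivity analyses when more than 10% of a variable is missing.

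**The concern.** A paired test of change from baseline needs a baseline value for every patient who enters it. The written schedule gives D-dimer at two follow-up visits, and the standardized assay and unit are stated for those visits. If no acute sample were collected, the test could not be run. If acute values came from routine records, they might have been drawn at different points relative to heparin start. Section 4.1 admits patients through the outpatient clinic and by referral, and under Section 4.2 the DOAC is started no earlier than day 5 of heparin. A pre-heparin admission value and a value drawn at enrolment after DOAC start are therefore both possible readings of baseline.

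Under complete-case analysis, patients without a baseline value would leave the test, and the mean change would describe an unplanned subset. At stake are the size, comparability and representativeness of one secondary estimate. Each patient is their own control, so loose timing of the first sample does not by itself create a decline.

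**Working it through.** The protocol gives no D-dimer mean, SD, effect size or power, so there is no figure of its own to reproduce. The check is mainly a reading of the sections against each other, followed by a bound on the precision at stake.

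**Reading the sections together**

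1. *Section 5.1.2 against Section 6.* Section 5.1.2 groups endpoints by when they are assessed. A reference value taken at the start is not an endpoint assessment and would not normally appear in such a list. The text does not restrict sampling to 3 and 6 months, so Section 6 does not contradict it.
2. *Secondary Objectives.* The 3- and 6-month introduction also covers mortality and venous recanalization, which Section 5.1.2 places at 6 months. It is a shared heading and carries little weight as a D-dimer schedule.
3. *Section 5.2.* The baseline list opens as a set of examples. The list of follow-up items in the same section also omits D-dimer, although Section 5.1.2 clearly plans it at those visits. Absence from Section 5.2 is therefore weak evidence that a value is not collected.
4. *Section 3.* Data collection spans the acute admission and later follow-up, and an acute-phase laboratory value fits within that. The schematic could also show a baseline sample, and its absence from the text at hand is no defect of the plan.
5. *Data source.* The study abstracts routine-care records. A value already in the hospital record needs no protocol-scheduled draw. The protocol does not say, however, that an admission D-dimer is routine.

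**Bounding the precision**

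Inputs: N = 69, the minimum in Section 5.3; the 10% trigger in Section 6; a missing share f, which is assumed because the protocol gives none.

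Trigger: 6/69 = 8.7% stays below 10%, and 7/69 = 10.1% exceeds it. With exactly 69 patients, seven missing baseline values would already call for sensitivity analyses.

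Pairs: n = 69 × (1 − f). Half-width of the 95% confidence interval for the mean change, in SDs of the change: t(0.975, n − 1)/√n.

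| Assumed f | Pairs n | Half-width (SD of change) |
|---|---|---|
| 0 | 69 | 0.240 |
| 0.1 | 62 | 0.254 |
| 0.3 | 48 | 0.290 |
| 0.5 | 34 (34.5 before rounding) | 0.349 |

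Losing half the pairs widens the interval by a factor of 0.349/0.240 = 1.45. These figures are for a mean change; Section 6 says only that paired tests will be used, so they illustrate scale and predict nothing.

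**Timing**

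The 5 to 15 days in Section 4.2 bound the start of the DOAC after heparin. They do not bound blood sampling or enrolment, and a patient entering through the outpatient clinic could be enrolled after day 15. The protocol therefore gives no numerical range for the timing of a baseline D-dimer.

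**The case for a change.** The best case for a change is that an analysis plan can choose among values already collected but cannot supply a sample or case-report field that was never foreseen. Recruitment was planned from June 2025, and acute values not recorded with date and assay may be hard to recover. Two analysts could take baseline as diagnosis, heparin start, DOAC start or enrolment and report different mean changes. The 10% trigger addresses missing values and does nothing for mixed timing among values that are present.

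Part of this stands: no shown text names a baseline D-dimer, and a sentence naming it would help. The rest is weaker. The argument about an unforeseen sample loses force in a study that draws on routine records. Use of differing assays is conjecture: Section 4.1 says that referred patients are included and does not say that outside laboratory results will be used, and the study has a single centre.

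The possible remedies gain little. Adding an admission value presumes that one is routinely taken; if it is, the baseline largely exists already and only wording is missing. Restricting the test to 3 versus 6 months gives up the acute-to-follow-up contrast, which is the more informative one. A mixed model on log D-dimer would be a preference.

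**Conclusion.** No change to the plan is called for. Section 6 relies on a baseline D-dimer that the shown text leaves undefined, but nothing in the protocol rules one out. An analyst would fill the gap sensibly with the acute-phase value, state which value was used, and report the number of pairs. That is detail commonly settled in a statistical analysis plan, which is not at hand.

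The reach is one secondary endpoint. The primary endpoint is unaffected, and no sample size or decision rests on D-dimer. The precision at risk is modest even with half the baseline values absent.

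This conclusion assumes that acute-phase D-dimer values exist in the hospital records for most patients, which the protocol does not confirm. If they turned out not to exist, the 3- to 6-month comparison would still be available from the measurements that Section 5.1.2 schedules, so the endpoint would not be lost.
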